7.4.3 Laboratory Data

Shift tables (e.g., tables that show the number of subjects who are low, normal, or high at baseline versus each post-baseline scheduled assessment) will be produced for the Safety Analysis Sets.

All data will be displayed in patient data listings for Safety Analysis Sets.

7.4.4 Vital Signs

Vital sign measurements (pulse rate, systolic blood pressure, diastolic blood pressure, body temperature, respiratory rate, weight, and height) during the study will be displayed in a vital signs listing.

7.4.5 Electrocardiogram (ECG)

ECG data (Heart Rate, PR Interval, QRS Interval, QT Interval, and QTcF Interval) will be listed.

Statistical Analysis Plan

Protocol No. ANB019-206
Last Revision Date: 12JAN2022

(Page 24 of 28)

7.4.6 Other Safety Assessments

Chest X-ray, physical examination, TB test results, pregnancy test, viral serology, and FSH will be presented in listings for the Safety Analysis Set. Abnormal result of physical examination will be listed. No AEs of special interest will be defined.

8. CHANGES FROM METHODS PLANNED IN THE PROTOCOL

Due to termination of study, the analysis of efficacy and safety variables will be significantly reduced from the originally planned analyses in the study protocol.

9. STATISTICAL SOFTWARE

The statistical software to be used for generation of the tables, listings, and figures is statistical analysis system® (SAS) version 9.4 or higher.

11. APPENDIX 1 DATA HANDLING RULES

The following table presents the algorithms to be used in SAS to calculate the derived variables, including rules for handling other missing data or partial dates, or irregular/unexpected data issues.

Category	Description	Data Handling Rules
1. Medical History	Medical History Beginning Date of Condition	
Missing day of begin date of condition will be imputed as the 1st of the month for the purpose of computing the onset day.Missing month of begin date of condition will be imputed as June for the purpose of computing the onset day
	Medical History End Date of Condition	
Missing day of end date of condition will be imputed as the 30th of the month for the purpose of computing the onset day.Missing month of end date of condition will be imputed as June for the purpose of computing the onset day
2. First and Last Treatment Dates	date/time of first and last dose of a study treatment	The date and time (24 hr. clock) of the first dose of study treatment will be taken from the Dosing eCRF. The date of the last dose of study treatment will be the last date of dosing from the Dosing eCRF for the treatment.
3. Last Visit Date	Date of Last Visit	Date of last visit according to the Visit eCRF.
4. Last Study Participation Date (SDTM variable, typically named RFPENDTC)	Last Study Participation Date (SDTM variable, RFPENDTC), where SDTM denotes Study Data Tabulation Model	Last study participation date is defined as last known date of contact which would be the later of the following dates: last visit date, date of the last dose, date of study completion or discontinuation, or death date.
5. Study Day Definitions	Study Day for assessment/event which occurs on or after the start of study treatment	Study Day = Date of assessment/event – date of the first dose of study treatment + 1.
	Study Day for assessments/events on days prior to the first dose of study treatment in the study	Study Day = date of assessment/event – first dose date of treatment in the study.
	Study Day of Randomization	Study Day of Randomization = date of randomization – date of the first dose of study treatment in the study + 1. Study Day is 1 if baseline day is on the day of randomization.
	First Dose Day	First Dose Day in the study is defined as the study day of the first dose of study treatment in the study (Study Day 1).

Statistical Analysis Plan

Protocol No. ANB019-206

Last Revision Date: 12JAN2022

(Page 26 of 28)

Category	Description	Data Handling Rules
	Last Dose Day	Last Dose Day in the study is defined as the study day of the last dose of study treatment in the study (defined as the last date of dosing from the Dosing CRF pages).
	Last Study Day	For subjects who did not receive study treatment in the study (e.g., Non-Randomized subjects) , Last Study Day is defined as (the later of the last visit date and the date of study completion or discontinuation from the End of Study CRF) – Date of Screening Visit + 1. For subjects who received study treatment in the study , Last Study Day is defined as (the later of the last visit date and the date of study completion or discontinuation from the End of Study CRF) – first dose date in the study + 1.
	Days Since Last Dose for event (e.g., Death)	Days Since Last Dose is defined as date of event – date of last dose of study treatment.
6. Duration of event	The duration of any event	The duration of any event is defined as (stop date – start date + 1).
7. Prior and concomitant, medication / treatment	Prior and concomitant medication/treatment	
1. Prior medication/treatment is any medication/treatment stopped prior to the first dose of study treatment (or the date of the randomization visit, Day 1, if the date of the start of study medication is missing). Medication/treatment continued into the treatment period will not be considered prior.2. A medication/treatment will be identified as a concomitant medication/treatment if any of the following are true:
o The start date or the end date is on or after the date of the start of study treatment (or the date of randomization, Day 1, if missing).o The medication/treatment is checked as 'Ongoing', and the start date of the medication/treatment is prior to the first dose of study treatment (or the date of the randomization visit, Day 1, if the date of the start of study medication is missing).o The start date and the end date are both missing
8. Adverse event	Treatment-emergent adverse event	If the AE start date is partial/missing, then 
• If AE start date is completely missing, then the AE is considered as treatment-emergent.• If both AE start month and day are missing and AE start year is the same or after the first dose year, then the AE is considered as treatment-emergent.• If AE start day is missing and AE start year and month are the same or after the first dose year and month, then the AE is considered as treatment-emergent.

Statistical Analysis Plan

Protocol No. ANB019-206

Last Revision Date: 12JAN2022

(Page 27 of 28)

Category	Description	Data Handling Rules
		Missing/incomplete (partial) AE start and end dates will not be imputed for data listings.
	Missing relationship to study drug	For TEAE summary by relationship, a TEAE with a missing relationship to study drug will be considered as related.
9. Vital Signs	Multiple assessments for the same visit	If there are multiple vital sign values for the same parameter at a given visit, the last value will be chosen for analysis.

Statistical Analysis Plan

Protocol No. ANB019-206
Last Revision Date: 12JAN2022

(Page 28 of 28)

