8.2.1.4 TIME PERIOD AND FREQUENCY FOR EVENT ASSESSMENT AND FOLLOW-UP

The occurrence of an AE or SAE may come to the attention of study personnel during study visits and interviews of a study subject presenting for medical care, or upon review by a study monitor.

All AEs including local and systemic reactions will be captured on the appropriate eCRF. Information to be collected includes event description, date of onset, clinician's assessment of severity, seriousness, relationship to study treatment (assessed only by those with the training and authority to make a diagnosis), action taken, and outcome of the event. All AEs occurring while on study must be documented appropriately regardless of relationship (see [Section 8.2.1.3.2](#)). All AEs will be followed to adequate resolution.

Study site personnel will note the occurrence and nature of each subject's medical condition(s) present prior to the informed consent signature in the appropriate section of the source document and eCRF. During the study, site personnel will note any change in the condition(s) and the occurrence and nature of any AE. Care will be taken not to introduce bias when detecting AEs and/or SAEs. Open-ended and nonleading verbal questioning of the subject is the preferred method to inquire about AE occurrences.

DocuSign Envelope ID: E4BE9C16-DB1E-4354-B874-2109B7254DAA

Efficacy and Safety of ANB019 in Subjects with Ichthyosis
Protocol ANB019-206

Version 1.0
30 October 2020

Should a subject experience an AE at any time after the screening visit informed consent signature until the end of participation in the study, the event will be recorded as an AE in the source document and eCRF. Any SAE related to the study participation (eg, screening procedure) will be recorded in the source document and eCRF from the time consent is given to participate in the study until the end of participation in the study (EOS/ET visit).

Investigators are not obligated to actively seek AEs or SAEs after conclusion of the study participation. However, if the Investigator learns of any SAE, including a death, at any time after a subject has been discharged from the study, and he or she considers the event to be reasonably related to the study treatment or study participation, the Investigator must promptly notify the pharmacovigilance unit.

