9.4.8.1 ADVERSE EVENTS AND SERIOUS ADVERSE EVENTS

A TEAE is defined as:

- A new event that occurs during or after first dose of study treatment or,
- Any event present at Baseline that worsens in either intensity or frequency after first dose of study treatment.

Adverse events will be coded using the MedDRA and only TEAEs will be summarized. Number of events and percentage will be tabulated by preferred term (PT) and system organ class (SOC). Multiple occurrences of an AE for a subject will only be counted once per SOC and PT. Percentages will be determined relative to the subjects in the safety analysis set for the given treatment arm.

If the intensity or seriousness of the AE changes, the overall intensity or seriousness will be the maximum intensity or seriousness of the multiple occurrences. The TEAEs, SAEs, TEAEs leading to treatment discontinuation, and TEAEs leading to withdrawal of subject will be tabulated for each treatment arm.

All AE data will be listed for each subject.

Summaries over SOC and PT of TEAEs, TEAEs leading to death, SAEs, and TEAEs that led to discontinuation from the study or study treatment will be presented by treatment. Summaries will also be presented by relatedness to the study treatment and the severity of the TEAE.

9.4.8.2 12-LEAD ELECTROCARDIOGRAM, VITAL SIGNS, AND CLINICAL SAFETY LABORATORY TESTS

Summaries and listings of data for vital signs and safety laboratory tests result (hematology, biochemistry, and urinalysis) will be presented. Appropriate descriptive statistics will be summarized for the observed value at each scheduled assessment and for the corresponding change from Baseline.

For hematology and biochemistry tests, listings of subject data will also flag up any abnormal or out-of-range values. Clinically significant changes in the laboratory test parameters will be summarized and listed. Hematology and biochemistry data will be reported in System International units.

Descriptive statistics will be used to present the safety outcomes including, weight, BMI, 12-Lead ECG, vital signs, and clinical laboratory test results.

Change from Baseline will also be summarized for vital signs, and clinical laboratory tests results.

All ECG data results (normal/abnormal) will be summarized using frequency and percentage, and parameter values will be summarized descriptively. Clinically significant abnormalities will be presented in by-subject listings.

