6.3.2 Adverse Events

AEs experienced by the subjects will be collected throughout the entire study and will be coded using the version of the MedDRA specified in the approved Data Management Plan. Analysis of adverse events will be carried out on the Safety Analysis Set.

An adverse event is considered treatment-emergent if the date of onset is during or after first dose of study treatment, or if the AE present at baseline that worsens in either intensity or frequency after first dose of study treatment. An adverse event that begins on the same date as the first dose of study treatment is treatment-emergent if the AE begins on or after the time of first dose or if the time of AE onset is unknown.

The severity of AEs will be evaluated as “Mild”, “Moderate”, and “Severe” using the criteria specified in [Section 8.2.1.3.1](#) of the study protocol.

AEs will be classified as related, possibly related, unlikely to be related, or unrelated to study treatment using the criteria specified in [Section 8.2.1.3.2](#) of the study protocol.

Adverse events will be categorized as serious or non-serious using the definition specified in [Section 8.2.1.2](#) of the study protocol.

Events with Partial Onset Dates

All treatment-emergent adverse events (TEAEs) will be included in the tabulations regardless of the completeness of the onset dates. Partial dates will be imputed in order to determine if an AE is treatment-emergent using the imputation rules in [Appendix 1](#); however, imputed dates will not be provided in the data listings.

Uncoded Events: Before the database lock, uncoded events will be assigned the string “UNCODED” as the body system, and the verbatim term will be used as the preferred term, so they can be included in the summary tables. In the final dataset, all the adverse events will have been coded.

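### SAP Appendix 1 item 8 ignores the AE end date, so some adverse events recorded as over before the first dose are counted as treatment-emergent

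*SAP*

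**What the plan says.** SAP Appendix 1, item 8, has three rules for an AE whose start date is missing or incomplete. Each ends in the same classification, treatment-emergent:

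- Start date wholly missing: "If AE start date is completely missing, then the AE is considered as treatment-emergent".
- Only the year known: "If both AE start month and day are missing and AE start year is the same or after the first dose year".
- Year and month known: "If AE start day is missing and AE start year and month are the same or after the first dose year and month".

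End dates appear in item 8 once, and only for display: "Missing/incomplete (partial) AE start and end dates will not be imputed for data listings".

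SAP 6.3.2 makes the appendix decisive: "Partial dates will be imputed in order to determine if an AE is treatment-emergent using the imputation rules in" Appendix 1. The same section gives the definition that the rules are meant to serve: "An adverse event is considered treatment-emergent if the date of onset is during or after first dose of study treatment", or an event already present at baseline gets worse after that dose. Protocol 9.4.8.1 has the same two limbs, the first being "A new event that occurs during or after first dose of study treatment or".

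Collection starts before dosing. Protocol 8.2.1.4 sets the window over which AEs must be recorded: "Should a subject experience an AE at any time after the screening visit informed consent signature until the end of participation in the study". Protocol 8.2.1.5 lists the stop date among the items entered in the eCRF.

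**The concern.** An AE that was over before the first dose meets neither limb of the definition. Its onset was before dosing, and it could not worsen afterwards. If the start date is incomplete but the end date is known, the record already shows that the event is not treatment-emergent. Item 8 does not look at that evidence. This is a stated rule that gives the wrong answer in an identifiable case, not a matter of missing detail.

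The AE tables carry much of what remains to be summarised. SAP 7.3 drops the efficacy analysis, SAP 6.4 drops PK, immunogenicity and IgE, and SAP 7.4.2 lists all AEs but tabulates only TEAEs. A screening event that passes the rule enters the overview table and the table by system organ class (SOC) and preferred term (PT), in whichever arm it falls.

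**Working it through.** The plan gives no figure on this point, so there is none to reproduce. The check is to apply the rules as written and compare them with the definition.

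**1. Is there an end-date check anywhere else?** SAP 6.3.2 adds none. Its one refinement concerns events that start on the day of first dose. The footnotes to the TEAE table shells repeat the definition only, and Protocol 9.4.8.1 has none. By contrast, Appendix 1 item 7 does use the end date for medications: a drug stopped before the first dose is prior, and with no dates to go on the default to concomitant requires both start and end to be missing.

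**2. Worked example.** Assume a first dose on 15 June 2021.

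| Recorded start | Recorded end | Item 8 as written | With an end-date check |
|---|---|---|---|
| missing | 10 June 2021 | TEAE | not TEAE |
| 2021 | 10 June 2021 | TEAE | not TEAE |
| June 2021 | 10 June 2021 | TEAE | not TEAE |
| May 2021 | 10 June 2021 | not TEAE | not TEAE |
| missing | 20 June 2021 | TEAE | TEAE |
| missing | missing | TEAE | TEAE |

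The first three rows contradict the definition. The fourth shows that a partial start date whose known part is earlier than the first dose is handled correctly. The last two show that the check leaves the default alone where timing is unknown.

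**3. How far the rule reaches within the affected class.** This is an illustration under assumptions: a first dose on each day of 2021, and a one-day AE 1 to 30 days earlier with its end date fully known. That gives 365 × 30 = 10,950 cases.

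- Start wholly missing: all are labelled TEAE, 100%.
- Year only: the exceptions are January doses with onset in the previous year, 30 + 29 + … + 1 = 465 cases. (10,950 − 465) / 10,950 = 95.8%.
- Year and month: cases in the first-dose month number 465 for each 31-day month, 435 for each 30-day month and 378 for February. (7 × 465 + 4 × 435 + 378) / 10,950 = 5,373 / 10,950 = 49.1%.
- Complete start date: 0%.

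With the check, all four are 0%. These percentages are conditional on the missing-date pattern and on a known pre-dose end. They are not error rates for the trial.

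**4. Effect of one misclassified subject.** SAP 7.4.2 counts a subject once per SOC and once per PT. An extra event therefore moves the overall, SOC or PT incidence only if the subject has no other TEAE at that level. The shift is then 1/n. At the planned arm sizes (SAP 3.4), 1/16 = 6.25%, or 6.3 points, and 1/8 = 12.5 points. The bracketed event counts in the table shells would rise by one in any case.

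**The case against.** The case against giving this weight is strong. The error needs three things together: onset before dosing, an incomplete start date, and an end date known to be before dosing. Protocol 8.2.1.4 and 8.2.1.5 require onset and stop dates, and Protocol 10.1.8 and 10.1.9.1 have missing data queried with the site. Nothing in the documents suggests that such a record exists. A default to treatment-emergent is the usual cautious choice, and it adds events without hiding any. Listing 16.5.1 prints the start date, the end date with study day, and the treatment-emergent flag together, so a reader could spot the case. All of this stands, and it limits the size of the point. It does not rescue the rule, because caution is warranted when timing is unknown and here a recorded date settles it. Nor would a later recurrence be lost: Protocol 8.2.1.4 asks for the onset and duration of each episode of an intermittent AE.

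Three stronger readings are tempting and are not supported:

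- **That about half of screening AEs with a missing start day are miscounted.** The share of screening days that fall in the first-dose calendar month is near one half. That share also covers events with a missing end date, ongoing events and events ending after the first dose, for which the default is defensible.
- **That one subject could move an arm by 50 points.** That needs an arm with two treated subjects. The study was terminated for low enrolment (SAP 1), so arms below plan are plausible, but the treated number is not given.
- **That such events would also be counted as related.** Protocol 8.2.1.3.2 has the investigator judge relationship with timing in view. Relatedness by default under item 8 would require the relationship field to be missing as well.

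**Conclusion.** The point holds as a narrow defect in a stated rule. It affects AEs with a wholly missing start date, or a partial start date whose known part equals or follows that of the first dose, when the recorded end date is before the first dose. AEs with a complete start date, or with a known earlier start year or month, are classified correctly.

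The number affected cannot be estimated from the documents and is probably small. The direction is known: over-counting only. The 6.3 and 12.5 point shifts assume that the arms reached their planned size and that the subject has no other TEAE at the level concerned; with fewer treated subjects the shift per subject is larger. The change is worth making because the TEAE tables are among the few summaries left, and the correction uses data already collected.

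**What to change.** In SAP Appendix 1 item 8, ahead of the three rules, add: *If the AE end date is known to be before the date of first dose (a complete end date earlier than the first dose, or a partial end date whose known year, or year and month, is earlier than that of the first dose), the AE is not treatment-emergent. If the end date is missing, the event is ongoing, or the end date is partial and overlaps the first-dose month or year, the rules below apply.*

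No clause about worsening is needed, since an event that has ended before the first dose cannot worsen after it. An end date on the day of first dose is not before it, so the same-day rule in SAP 6.3.2 is untouched. A record whose known start is later than the first dose but whose end is earlier contradicts itself and should go to data query.

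In SAP 6.3.2, state that partial dates are classified under Appendix 1 rather than imputed, because item 8 assigns a status and never produces a date.

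The cost is two small text edits and one condition in the AE derivation. No new data are needed.

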where: PGNAME = SAS program name. Version will be replaced by “Draft” or “Final”.

Title

At least three (3) lines should be reserved for the whole title. The first line is for the TFL number (i.e., title index #); the second line is for the actual title (title); and the third line is reserved for the analysis population descriptor (population). All titles should be centered, as shown in the following example:

Table 3.1
Demographics
Safety Analysis Set

Footnotes

- In general, a footnote serves as a brief explanation/clarification/definition/concept of a flag symbol or a character, an abbreviation, a terminology, etc., that appears in or related directly to the displayed content of a TFL. Detailed/technical elaboration of, for example, a mathematical/statistical formula, a statistical term/test, or an algorithm for deriving a parameter value, should be addressed in the text of the statistical analysis plan (SAP).
- All footnotes should follow immediately after a horizontal solid line. There should be one and only one space between the last footnote and the footer.
- Each line of a complete footnote should end with a period. When a footnote needs more than 1 line, one (1) period is needed.
- If a footnote is very long – i.e. is longer than the length (per page) of the main body of a table or listing, then the footnote will be shown only on the final page of the table or listing.

Page Layout

- All output should be in landscape orientation. A margin of 1.5, 1, 1, and 1 inch should be on the top, right, left, and bottom, respectively.
- All efforts should be made to present all Treatment groups in one page.
- When 3 or more Treatment groups are designed for a study and if it is not possible to fit all of them in one page, the 4th and 5th treatment groups should be displayed on the 2nd page, etc. The Study Biostatistician will pre-determine the order for the display of the treatment groups.

Page Format

- There should be a solid line at the top of the tables and listings just below the title.

ANB019
Protocol ANB019-206

Version 1.0
12JAN2022
Page 5 of 65

- There should be a solid line just below the column headings that runs completely across the width of the tables and listings.
- There should be a solid line at the bottom of the tables and listings just above the footnote(s) on every page.

Font

- The default font to be used in the actual study tables/listings should be Courier New 8 point which is approximately equivalent to the acceptable font size of Times New Roman 9-10 in accordance with the FDA's guidance on Electronic Common Technical Document Specification.
- The use of Courier New 7 point is optional for some tables/listings and will be determined at the study level by the Study Biostatistician and Study Programmer. However, it is recommended that this option be used primarily for data listings.

Descriptive Statistics

By default, descriptive statistics in this template covers: n, Mean, Median, Standard Deviation (SD), Minimum (Min), and Maximum (Max). Unless otherwise specified in the actual table shells, the mean, standard deviation, standard error of the mean, and median should be displayed to one more decimal place than the original data. The standard error of the mean will be displayed with at least 2 significant digits for efficacy tables.

Rounding for Percentage

Unless specified in the actual table shells for a study, all percentages will be rounded to 1 decimal place in all TFLs. If the percentage is less than 0.1 but greater than 0 then print "<0.1". If the percentage is greater than 99.9 but less than 100 then print ">99.9".

Unless specified in the actual table shells for a study, p-values will be presented with 4 decimal places. If the p-value is less than 0.0001 then print "<0.0001".

Alignment of Decimals

- It is recommended that all the decimal places be aligned in summary tables, as shown in the following example:

Decimal Align	
n	xxx
Mean	xx.xx
SD	xx.xx
Median	xx.xx
Min, Max	xx.x, xx.x

The example above is intended only to show how decimal places will be aligned. It is not intended to show how many decimal places will be given for various fields for various tables. It is also not intended to show which fields will be displayed on which lines.

- When numbers with decimal points are included in brackets (e.g., percentages), have the brackets aligned to the right and then padded to allow for all possible percentages and then the left brackets will also be aligned. For example:

Brackets Align

(99.9)	(xx.x)
(9.9)	(x.x)

- It is recommended that all column entries in a summary tables and listings are aligned to the center.

ANB019
Protocol ANB019-206

Version 1.0
12JAN2022
Page 6 of 65

- Columns for text fields are all left justified. Columns with whole numbers are all right justified.
